3 OBJECTIVES AND ENDPOINTS

Table 2 - Objectives and endpoints

Objectives	Endpoints
Primary 
Phase 1: To characterize the safety and tolerability of isatuximab in kidney transplant candidates.Phase 2: To evaluate the efficacy of isatuximab in desensitization of patients awaiting kidney transplantation.	
Adverse events (AEs)/serious adverse events (SAEs) and laboratory abnormalities.Response rate (RR) defined as the proportion of participants meeting at least one of the predefined desensitization efficacy criteria, from baseline up to 26 weeks after treatment period, measured by single antigen bead (SAB) assay per central laboratory assessment as follows:
Reduction in calculated panel reactive antibodies (cPRA) resulting in at least 100% increase of likelihood of finding a compatible donor (for target cPRA, see Section 10.9).Reduction in antibody titer ($\geq 75\%$ reduction from baseline) to achieve target cPRA (see Section 10.9).Elimination of ≥ 1 anti-HLA-antibody (ie, mean fluorescence intensity [MFI] reduced to <2000) as measured by a SAB assay, for antibodies with baseline MFI ≥ 3000.
Secondary 
Phase 2: To characterize the safety profile of isatuximab in kidney transplant candidates.To characterize the pharmacokinetic (PK) profile of isatuximab in kidney transplant candidates.To evaluate the immunogenicity of isatuximab.To assess the overall efficacy of isatuximab in desensitization of patients awaiting kidney transplantation.	
AEs/SAEs, and laboratory abnormalities.PK parameters of isatuximab (see Table 7)Incidence of anti-drug antibodies (ADA) against isatuximab.Duration of response (DoR) per central laboratory assessment.Proportions of participants and duration achieving target cPRA per local laboratory assessment.Number of anti-HLA-antibody with baseline MFI ≥ 3000 reduced to <2000 as measured in a SAB assay per central laboratory assessment.Transplantability including time to first transplant offer, time to transplant, and number of transplant offers, if applicable.Time to first AMR episode and rate of AMR, if applicable.Graft survival at 6 months post-transplant, if applicable.

Objectives	Endpoints
Tertiary/exploratory	
• To assess other preliminary efficacy of isatuximab in desensitization of patients awaiting kidney transplantation.	[REDACTED] [REDACTED] [REDACTED] [REDACTED] [REDACTED] [REDACTED] [REDACTED] [REDACTED] [REDACTED] [REDACTED] [REDACTED] [REDACTED]
• To assess the biological effects of isatuximab on immune cell populations and identify potential predictive and/or PD biomarkers	[REDACTED] [REDACTED] [REDACTED] [REDACTED] [REDACTED] [REDACTED]
• To perform PK/PD analysis.	[REDACTED] [REDACTED] [REDACTED]

3.1 APPROPRIATENESS OF MEASUREMENTS

Each of the efficacy and safety assessments chosen for use in this study is considered well established and relevant in the renal transplant setting. In addition, suitable steps have been built into each of these assessments to ensure their reliability and accuracy and to minimize any risks to patient safety.

Safety and tolerability are the primary objectives of the Phase 1 with endpoints including AEs/SAEs and laboratory abnormalities. The safety objective is extended as a secondary objective for Phase 2. Monitoring of safety data is described in detail in [Section 8.3](#) and [Section 10.3](#).

Efficacy of isatuximab in desensitization is the primary objective for Phase 2. Participants are considered as responders if meeting at least one of the predefined desensitization efficacy criteria as outlined in [Section 3](#). The predefined desensitization efficacy criteria are designed to capture the ability of isatuximab in removing/reducing circulating anti-HLA antibody. Calculated panel reactive antibody is a standardized parameter to estimate the unacceptable risk against the national donor population, based upon unacceptable HLA antigens which the transplant candidates have antibodies against. The SAB assay is the most widely accepted method for precisely identifying the anti-HLA antibodies due to its much-improved sensitivity and specificity compared to older methods such as cytotoxicity or flow cytometry. The assay is considered to be acceptable as a semi-quantitative assay (negative or positive), with MFI of <2000 may be considered negative at multiple kidney transplant centers. The MFI variability has been reported as up to 62%; while standardized operating procedure could reduce variability to <25% even across centers and with different reagents ([52](#), [53](#)). The TED16414 study utilizes a central laboratory for primary efficacy assessment and the MFI variability is expected to be <25%. As a conservative approach to mitigate false positive RR, the third predefined efficacy criterion (ie, elimination of ≥ 1 anti-HLA antibody) is only applicable to antibodies with baseline MFI ≥ 3000 to account for possible assay variability. Moreover, reduction in anti-HLA antibody strengths are being evaluated by antibody dilution (ie, second criterion) instead of quantifying MFI values ([54](#), [55](#)).

Duration of response (assessed both locally and centrally) is included as a secondary endpoint to address potential antibody rebound concern, which is commonly observed with current desensitization protocols. If applicable, transplantability and post-transplant outcomes will also be captured as secondary endpoints.

4 STUDY DESIGN

4.1 OVERALL DESIGN

This is a Phase 1b/2 open-label, non-randomized, multi-center study to evaluate the safety, PK, and preliminary efficacy of isatuximab in patients awaiting kidney transplantation. The study will be conducted in 2 phases (see [Figure 1](#) for study design schema):

Phase 1 (safety run-in)

A minimum of 6 safety evaluable participants with cPRA $\geq 80\%$ will be enrolled at the dose level to be tested without interruption in Phase 1. In order to be considered as safety evaluable, participants must have received at least 90% of the planned cumulative doses of the first cycle (unless they discontinue IMP due to pre-defined unacceptable toxicity).

Pre-defined unacceptable toxicity is defined as any verified Grade 4 AEs or laboratory abnormalities (except IRs) occurring during the first cycle of treatment, unless solely due to the underlying disease or due to a cause obviously unrelated to IMP, if confirmed by the Sponsor and recruiting Investigators.

The totality of the safety findings, including all AEs occurring during treatment, unless solely due to the underlying disease or due to a cause obviously unrelated to IMP, will be taken into consideration for confirming the Phase 2 dose. Phase 2 of the study will be initiated after 6 safety evaluable participants have completed first cycle observation period where the dose level is determined to be sufficiently well-tolerated.

If the SD is determined not to be sufficiently well-tolerated, 6 additional (minimum) safety evaluable participants will be enrolled at DL-1 (see [Table 4](#) for details on the dose levels and schedule for Phase 1).

Overall safety monitoring will also be performed throughout the conduct of the study.

Upon completion of the first cycle safety observation period for each participant enrolled in Phase 1, participants will continue study procedures until study completion (see “Duration of study period [per participant]” in [Figure 2](#)).

Phase 2

In Phase 2, two cohorts will be included:

Cohort A: Participants with cPRA $\geq 99.90\%$; active candidates on the kidney waitlist. Up to 6 participants with living donor can be enrolled into Cohort A.

Cohort B: Participants with cPRA 80.00% to 99.89%; active candidates on the kidney waitlist with no living donor cleared for donation.

The study will have a screening period of up to 28 days, a treatment period of up to 12 weeks, a site visit FUP of up to 26 weeks, and an extended FUP which include telephone contacts every 90 days and information collection until study cut-off, death, or lost to follow-up. The study cut-off is planned at 26 weeks after the last participant completes the treatment period, or when the last ongoing participant is lost to follow-up, whichever is earlier. The Sponsor may choose to extend the study cut-off date depending on the enrollment rate observed to facilitate adequate follow-up data collection. Participants who wish to proceed to transplantation when a compatible donor becomes available while on study must discontinue IMP immediately, and complete an E/D visit prior to transplantation if clinically feasible, and proceed to extended FUP. The study duration that involves site visit per participant (ie, screening, treatment, site visit FUP) will be approximately 42 weeks. The study duration including extended FUP per participant will be approximately 78 weeks (depending when the participant is enrolled).

Treatment period: The cycle duration is 28 days and a complete treatment period is comprised of 3 cycles of IMP treatment. Participants will continue treatment until receiving 3 cycles of IMP, unacceptable AE per Investigator's judgment, or participants' decision to stop the treatment.

Site visit FUP: Participants completing the treatment period and who are able to remain on study will return to the study sites for study procedures.

Extended FUP: The following participants will be followed-up every 90 days by phone calls, until study cut-off date, death, or lost to follow-up, whichever comes first:

- Participants who completed or discontinued from site visit FUP
- Participants who proceed to transplantation during treatment period or site visit FUP.

During extended FUP, specified information per protocol will also be collected by study site (see [Section 1.3](#)).

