	
increase of likelihood of finding a compatible donor (for target cPRA, see Section 10.9).
 
- Reduction in antibody titer ($\geq 75\%$ reduction from baseline) to achieve target cPRA (see Section 10.9).- Elimination of ≥ 1 anti-HLA-antibody (ie, mean fluorescence intensity [MFI] reduced to < 2000) as measured by a SAB assay, for antibodies with baseline MFI ≥ 3000.
Secondary	
	
• Phase 2: To characterize the safety profile of isatuximab in kidney transplant candidates.• To characterize the pharmacokinetic (PK) profile of isatuximab in kidney transplant candidates.• To evaluate the immunogenicity of isatuximab.• To assess the overall efficacy of isatuximab in desensitization of patients awaiting kidney transplantation.• AEs/SAEs, and laboratory abnormalities.• PK parameters of isatuximab (see Table 7)• Incidence of anti-drug antibodies (ADA) against isatuximab.• Duration of response (DoR) per central laboratory assessment.• Proportions of participants and duration achieving target cPRA per local laboratory assessment.• Number of anti-HLA-antibody with baseline MFI ≥ 3000 reduced to < 2000 as measured in a SAB assay per central laboratory assessment.• Transplantability including time to first transplant offer, time to transplant, and number of transplant offers, if applicable.• Time to first AMR episode and rate of AMR, if applicable.• Graft survival at 6 months post-transplant, if applicable.

Overall design:

This is a Phase 1b/2 open-label, non-randomized, multi-center study to evaluate the safety, PK, and preliminary efficacy of isatuximab in patients awaiting kidney transplantation. The study will be conducted in 2 phases (see [Figure 1](#) for study design schema):

Phase 1 (safety run-in)

A minimum of 6 safety evaluable participants with cPRA $\geq 80\%$ will be enrolled at the dose level to be tested without interruption in Phase 1. In order to be considered as safety evaluable, participants must have received at least 90% of the planned cumulative doses of the first cycle (unless they discontinue investigational medical product [IMP] due to pre-defined unacceptable toxicity).

Pre-defined unacceptable toxicity is defined as any verified Grade 4 AEs or laboratory abnormalities (except infusion reactions [IR]) occurring during the first cycle of treatment, unless

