6.6.2 Dose delay and dose omission

Within a cycle, the treatment window is ± 1 day for each of the weekly administrations and ± 2 days for each of the Q2W administrations. Within a cycle, a dose is deemed to have been delayed if the treatment is ≥ 2 days beyond the theoretical day of treatment for weekly dose, or ≥ 3 days beyond the theoretical day of treatment for Q2W dose. The reason for dose delay must be captured. The participant will receive the next infusion/cycle after recovery from the AE.

If infusion has been delayed within a cycle, the next dose of IMP should be administered at the planned time interval between the 2 administrations (eg, if Cycle 1 Day 15 administration was administered on Day 17, the planned Day 22 should be administered on Day 24 ± 1 day).

Participants may have dose delay, cycle delay, or dose omission if an AE occurs and does not recover according to the following rules:

- In Cycle 1 (for weekly administration) if an AE occurs and the participant does not recover on the day of planned infusion or within the following 3 days, infusion of isatuximab (Day 8, Day 15, or Day 22) may be omitted.
- In Cycles 2 and 3:
 - For Day 1 infusions: If an AE occurs and the participant does not recover on the day of planned infusion, the cycle may be delayed up to a maximum of 2 weeks.
 - For Day 15 infusions: If an AE occurs and the participant does not recover on the day of planned infusion or within the following 7 days, infusion of isatuximab may be omitted.
- If the AE is not recovered within 14 days:
 - IMP may be delayed up to 56 days.
 - After a cycle delay of >14 days and ≤ 56 days, it is per Investigator's decision to restart the treatment or the IMP that is omitted, if a clear benefit from therapy is observed and after consultation with the Medical Monitor.
 - The IMP must be definitively permanently discontinued if the dose/cycle delay is longer than 56 days.

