6.6.3 General guidelines for the management of adverse events

Guidelines for isatuximab dose modifications and treatment discontinuation due to hematological and non-hematological AEs in general are outlined in [Table 5](#).

The final decision will be per Investigator's judgment for the best interest of the participant.

Table 5 - General management guidelines for adverse events

Adverse Event (NCI-CTCAE version 5.0 criteria)	Management of Isatuximab	Action and Guidelines
Hematological AE		
Grade 1, 2, 3	No change in dose	Participant should be given supportive care and monitored closely.
Grade 3 Thrombocytopenia lasting >7 days or associated with bleeding	Delay the dose/cycle until bleeding is controlled and platelet >50 000/mm ³ . Restart treatment with the same dose and schedule.	
Grade 4	Delay the dose/cycle until ANC >1000/mm ³ , or platelet >50 000/mm ³ , or hemoglobin >8 g/dL. Restart treatment with the same dose and schedule. Grade 4 lymphopenia: no change in dose.	Participant should be given supportive care and monitored closely. Permanent discontinuation should be considered if AE does not resolve/recover within 56 days of last infusion.
Febrile neutropenia and/or neutropenic infection	Delay the dose/cycle until fever and infection recovered and ANC >1000/mm ³ . Restart treatment with the same dose and schedule.	
Non-hematological AE		
Grade 1	No change in dose	Not applicable
Grade 2	Delay the dose/cycle until improves to Grade ≤ 1 or baseline. Restart treatment with the same dose and schedule.	If the treatment interruption is >14 days, before restarting the treatment, Investigator must discuss with the Sponsor; if it is determined that it is for the best interest of the patient, treatment may be restarted.
Grade 3	Delay the dose/cycle until improves to Grade ≤ 1 or baseline. Restart treatment with the same dose and schedule	
Grade 4	Permanently discontinue treatment for treatment related AEs. For treatment unrelated AEs, delay the dose/cycle until improves to Grade ≤ 1 or baseline. Restart treatment with the same dose and schedule.	If the interruption is longer than 56 days, the treatment must be definitively discontinued
Infusion Reaction: see Table 6 for management guideline		

Abbreviations: AE = adverse event, ANC = absolute neutrophil count, CTCAE = common terminology criteria for adverse events, IV = intravenous, NCI = National Cancer Institute

Guidance in case of hepatitis B reactivation occurring under study treatment

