9.3 POPULATIONS FOR ANALYSES

For purposes of analysis, the following populations are defined ([Table 8](#)):

Table 8 - Populations for analyses

Population	Description
Screened	All participants who sign the ICF.
All Treated	Includes all participants who receive at least 1 dose of isatuximab. This population is the primary population for the analyses of safety parameters, unless otherwise noted. All analyses using this population will be based on the dose level actually received.
Safety Evaluable (Phase 1)	Includes all participants enrolled in Phase 1 who receive $\geq 90\%$ planned cumulative doses of isatuximab within Cycle 1 (unless IMP is discontinued due to pre-defined unacceptable toxicity).
Efficacy Evaluable	Includes All Treated Population who fulfill the study eligibility criteria, with an evaluable baseline and at least 1 evaluable postbaseline efficacy assessment, and receive $\geq 75\%$ of planned cumulative doses. This is the primary population for efficacy analyses.
PK	Includes All Treated Population with at least 1 available concentration result post-treatment (whichever the cycle and even if dosing is incomplete) with adequate documentation of date and time of dosing and date and time of sampling.
ADA	Includes All Treated Population with at least 1 available ADA result (negative, positive, or inconclusive) post-treatment (whichever the cycle and even if dosing is incomplete).

Abbreviations: ADA = anti-drug antibody, ICF = informed consent form, IMP = investigational medicinal product, PK = pharmacokinetic.

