1 INTRODUCTION

1.1 STUDY DESIGN

This is a Phase 1b/2 open-label, non-randomized, multi-center study to evaluate the safety, pharmacokinetics (PK), and preliminary efficacy of isatuximab in patients awaiting kidney transplantation.

Patients sensitized to the human leukocyte antigen (HLA) with a high calculated panel reactive antibodies (cPRA) have low likelihood of finding a compatible donor. Currently no approved or standard therapy is available for desensitization. An effective desensitization therapy with a durable response has the potential to increase the likelihood for transplant candidates to find a compatible donor, reduce time on dialysis, and a better clinical outcome.

The study will be conducted in 2 phases (see [Figure 1](#) for study design schema).

Phase 1 (safety run-in)

As the safety profile of isatuximab is well-established, Phase 1 (safety run-in) is designed to characterize the safety and tolerability of isatuximab in patients with chronic kidney disease (CKD), and to confirm the Phase 2 dose in this patient population. A minimum of 6 safety evaluable participants with cPRA $\geq 80\%$ will be enrolled at the dose level to be tested without interruption in Phase 1. In order to be considered as safety evaluable, participants must have received at least 90% of the planned cumulative doses of the first cycle (unless they discontinue investigational medicinal product (IMP) due to pre-defined unacceptable toxicity).

Pre-defined unacceptable toxicity is defined as any verified Grade 4 adverse events (AEs) or laboratory abnormalities (except infusion reactions (IRs)) occurring during the first cycle of treatment, unless solely due to the underlying disease or due to a cause obviously unrelated to IMP, if confirmed by the Sponsor and recruiting Investigators.

The starting dose of IMP is 10 mg/kg QW for 4 weeks followed by Q2W. If the starting dose is determined not to be sufficiently well-tolerated, 6 additional (minimum) safety evaluable participants will be enrolled at dose level (DL) -1 (ie, 5 mg/kg QW for 4 weeks followed by Q2W) (see protocol Table 4 for details on the DLs and schedule for Phase 1).

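### The SAP 4.7 listing of Phase 1 pre-defined toxicities can leave out a participant who had one, and Protocol 9.4.2 and SAP 4.7 name different Phase 1 safety populations with no change declared

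*Protocol*

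**What the plan says.** **Definition.** Protocol 4.1: "Pre-defined unacceptable toxicity is defined as any verified Grade 4 AEs or laboratory abnormalities (except IRs) occurring during the first cycle of treatment". The synopsis (Protocol 1.1) has "any verified Grade 4 AEs or laboratory abnormalities (except infusion reactions [IR]) occurring during the first cycle of treatment", and SAP 1.1 has "Pre-defined unacceptable toxicity is defined as any verified Grade 4 adverse events (AEs) or laboratory abnormalities". None of the three mentions Grade 5. All three exclude events due only to the underlying disease or to an obviously unrelated cause, if the sponsor and recruiting investigators confirm this.

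**Safety-evaluable set.** Protocol Table 8 and SAP Table 3 require at least 90% of the "planned cumulative doses of isatuximab within Cycle 1 (unless IMP is discontinued due to pre-defined unacceptable toxicity"). Having the toxicity is not enough for the exemption; the drug must have been stopped because of it. Protocol 9.2 allows a Phase 1 participant below 90% to be replaced, on the same terms.

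**Management of Grade 4 events.** For haematological events, Protocol Table 5 delays dosing until recovery ("or hemoglobin >8 g/dL. Restart treatment with the same dose and schedule"), with one exception: "Grade 4 lymphopenia: no change in dose". Treatment-related non-haematological Grade 4 events require permanent discontinuation. In Cycle 1, if an event has not recovered by the planned day or within the next 3 days, Protocol 6.6.2 states that "infusion of isatuximab (Day 8, Day 15, or Day 22) may be omitted".

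**Analysis populations.** Protocol 9.4.2 assigns all Phase 1 safety analyses to the Safety Evaluable set. Protocol Table 8 says of All Treated: "This population is the primary population for the analyses of safety parameters, unless otherwise noted". SAP 4.7 lists the pre-defined toxicities on the Safety-evaluable set and runs the remaining safety analyses on All Treated. SAP 4.3.1 sends the Phase 1 primary endpoint to SAP 4.7.2 and 4.7.3.1, which fall under that All Treated rule. SAP 5.2, the appendix for changes to protocol-planned analyses, is marked not applicable, and the SAP version history does not mention the population.

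**The concern.** The toxicity listing exists to show which Phase 1 participants had a pre-defined unacceptable toxicity. It is built on a set that a participant can leave because of how that same toxicity was managed. The exemption is meant to prevent this, but it is tied to stopping the drug, whereas the protocol's own instruction for most Grade 4 haematological events is to delay and restart.

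The literal grade adds a second gap. If a fatal event is never verified at Grade 4, it does not meet the definition, so the exemption that depends on the definition does not apply either.

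The population difference is a separate point. A reader of Protocol 9.4.2 expects Phase 1 safety results on one set and a reader of the SAP expects another, and nothing tells either of them that the plan changed. Safety is the Phase 1 primary objective and the run-in may be as small as six participants, so one participant missing from a listing is noticeable.

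**Working it through.** The plan states no figure on this point to reproduce. The check is dose arithmetic followed by a comparison of sections.

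**1. What 90% means in Cycle 1.** Inputs: four weekly infusions at 10 mg/kg (starting dose) or 5 mg/kg (DL-1), from Protocol Table 4; the 90% threshold, from Protocol Table 8.

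| | Starting dose | DL-1 |
|---|---|---|
| Planned Cycle 1 dose | 4 × 10 = 40 mg/kg | 4 × 5 = 20 mg/kg |
| Threshold | 0.90 × 40 = 36 mg/kg | 0.90 × 20 = 18 mg/kg |
| One infusion omitted | 30/40 = 75% | 15/20 = 75% |

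At the starting dose the margin is 40 − 36 = 4 mg/kg, or 0.4 of one infusion. A single omission therefore fails the threshold at either dose level.

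**2. Case (a): haematological toxicity, one infusion omitted, treatment continues.** The event meets the definition. Table 5 calls for delay and restart, and 6.6.2 permits the omission. Dosing is 75%. The drug was not discontinued, so the exemption does not apply. The participant is outside the Safety-evaluable set, outside the SAP 4.7 listing, and replaceable under Protocol 9.2. All of the following must hold: the event is not lymphopenia, it has not recovered within 3 days of the planned infusion, and the optional omission is used. Delay alone does not lower the dose share if the infusion is later given.

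**3. Case (b): drug-related fatal event never verified at Grade 4.** Read literally, this is not a pre-defined toxicity at any point in the cycle. If it occurs before the Day 22 infusion, at most 3 of 4 infusions (75%) have been given and the exemption does not apply, so the participant is also outside the set. If it occurs after that infusion with full dosing, the participant is in the set but the event still does not meet the definition.

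**4. Populations side by side.**

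| Phase 1 output | Protocol 9.4.2 | SAP 4.7 |
|---|---|---|
| Pre-defined toxicity listing | Safety Evaluable | Safety-evaluable |
| AEs, SAEs, deaths, laboratory (through SAP 4.3.1) | Safety Evaluable | All Treated |

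The proviso in Table 8 does not reconcile the second row, because 9.4.2 does note otherwise for Phase 1.

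**5. Scale, with assumed counts.** Suppose 7 participants are treated, one is a case (a) participant, and that one is replaced. The listing then shows 0 of 6, where all treated would show 1 of 7 (14%). The documents give no rate for either case, and no rule in the plan uses this count.

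**The case against.** The strongest reply is that nothing depends on this listing. The Phase 2 dose is confirmed on the totality of safety findings (Protocol 4.1), the Study Committee can review Phase 1 data (Protocol 10.1.5), SAEs reach the sponsor within 24 hours (Protocol 8.3.1), and Phase 1 has no formal hypothesis (Protocol 9.1). That stands, and it limits the point to reporting. A reader might infer that a Phase 1 death could disappear from the report or that the dose decision could rest on an incomplete count. The documents do not support either: SAP 4.7.2 counts Grade 5 within Grade 3 or higher and summarises deaths, on All Treated.

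A reader might also infer that every death before Day 22 is missed. It is not. A fatal event first verified at Grade 4 already meets the definition, and deaths due to underlying disease or an obviously unrelated cause are excluded under either wording.

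Nor is the toxicity listing the only Phase 1 safety output. SAP 4.3.1 sends the Phase 1 primary endpoint to the All Treated analyses, and Protocol Table 10 says Phase 1 AEs and laboratory abnormalities will be listed. The remark in SAP 4.1 that Phase 1 summaries are optional follows a sentence about demographics and baseline characteristics, so it does not clearly cover safety.

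The SAP 4.7 sentence has an unmatched bracket and may have lost text. If the listing was meant to be wider, the same exclusion would apply to more content, so this does not remove the gap.

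On populations, Protocol 9.4 calls itself a summary and leaves populations to the SAP. The SAP's broader set is therefore permitted, and it is the better choice. What remains is that it departs from an explicit sentence in 9.4.2 and SAP 5.2 does not say so.

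**Conclusion.** Minor, and wrong as written. As specified, the SAP 4.7 listing can be incomplete for the events it is meant to show: in the narrow haematological case at 75% dosing and, on a literal reading of Grade 4, for a drug-related fatal event never verified at that grade. The Phase 1 safety population differs between Protocol 9.4.2 and SAP 4.7 and the difference is undeclared.

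The consequence is for reporting only. The AE tables would count the event but, as described, would not mark it as a Phase 1 pre-defined toxicity. The conclusion assumes that the Safety-evaluable definition and its exemption are applied as written, and for the fatal case that Grade 4 is read literally. How often either case would arise cannot be estimated from the documents.

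**What to change.** **SAP-only route.** In SAP 4.7, run the toxicity listing on all treated Phase 1 participants, include Grade 4 or 5 events, and add a Safety-evaluable flag. In SAP 5.2, record that Phase 1 safety is analysed on All Treated in place of the set named in Protocol 9.4.2, and that the listing covers Grade 5.

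**If the protocol is amended anyway.** Change 9.4.2 to All Treated for Phase 1. If the definition in Protocol 1.1 and 4.1 and SAP 1.1 is also changed to Grade 4 or higher, state the side effect: a participant whose drug stops because of a related fatal toxicity would become safety evaluable and count toward the required six, even with 75% of dosing or less. The SAP-only listing change avoids this.

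Leave the 90% rule, the replacement rule and the infusion-reaction exception as sponsor design choices. The exemption need not be widened to omitted doses, since participants with 75% of dosing would then count toward the six.

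**Cost.** Wording only, with no new data and no change to the dose decision. The listing will contain participants who do not count toward the six, so readers must use the flag.
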